Blood pressure will be closely monitored before and during NTG (or placebo) therapy (also see “Safety Assessments” section below). At in-person screening and baseline visits and at each in-person follow-up visit thereafter, participants will undergo two resting blood pressure measurements by trained coordinators using calibrated monitors. Additionally, orthostatic measurements of blood pressure and heart rate will be obtained. If visits are conducted by video with participants at home, trained coordinators will guide participants step-by-step and in real time in obtaining the above measurements using automated monitors distributed to participants in advance of the visit.

In the event that participants report blood pressure readings <90/60 or >180/110 in outside contexts despite normal readings in the study visit, or participants report symptoms suggesting hypo- or severe hypertension despite normal blood pressure readings in the study visit, they will be invited to undergo additional home or ambulatory blood pressure monitoring for more intensive assessment of blood pressure.

B. Severe anticipated side effects of NTG therapy

At each follow-up visit or phone call after initiation of NTG or placebo, blinded study coordinators will systematically assess for the following potentially severe side effects of NTG therapy: 1) headache severe enough to interfere with instrumental activities of daily living; 2) chest tightness or pain interfering with instrumental activities of daily living, and 3) syncope (fainting or loss of consciousness). If reported, these symptoms will be recorded on adverse event forms that will indicate date of onset, date of resolution, likelihood of relationship to treatment, actions taken in response to the event, and severity according to the Common Terminology Criteria for Adverse Events (CTCAE) scale from the National Cancer Institute (National Cancer Institute 2009) (see “Safety Assessments” section below). Participants will also be given the phone number for the study site and will be instructed to contact study staff in between study visits to report any chest pain suggestive of cardiac ischemia, syncope, or other severe anticipated side effects such as headache interfering with daily activities.

C. Unanticipated adverse events

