In addition to systematically eliciting selected anticipated adverse events as noted above, blinded study coordinators will assess for other unanticipated adverse events at each follow-up contact using the standardized question, “Have there been any changes in your health since your last visit?” Participants will also be given a telephone number that can be used to contact study staff to report any adverse events experienced in between scheduled study visits. Negative changes will be recorded as adverse events on standardized adverse event forms, with documentation of date of onset, date of resolution, likelihood of relationship to treatment, and actions taken in response to the event, and severity according to the CTCAE scale (National Cancer Institute 2009) (see “Safety Assessments” section below).

G.1.4 Demographic and clinical covariates

Structured questionnaires will collect data on the following variables in order to assess eligibility, characterize the study cohort, assess whether groups are comparable at baseline, and guide statistical adjustments in the event that significant differences between groups are detected at baseline:

- A. Sociodemographic history (date of birth, race/ethnicity, education, employment, marital/relationship status);
- B. Medical history (diagnosed medical conditions including coronary disease, diabetes mellitus, hypertension, hypercholesterolemia; use of prescription and OTC drugs);
- C. Reproductive/menopausal history (date of last menstrual period, number of periods in the prior 12 months, hysterectomy, oophorectomy, parity, age of onset of hot flashes, current and past use of hot flash treatments)
- D. Blood and urine testing: Follicle stimulating hormone levels will be measured in women under the age of 60 years with a history of hysterectomy without oophorectomy. Urine pregnancy testing will be performed in women who may still be of child-bearing potential.

G.2 Primary and Secondary Outcomes

- The primary outcome of this trial is *change in the average frequency of any hot flashes* from baseline to 4 and 12 weeks, as documented by symptom diaries.
- Secondary outcomes include changes in frequency of moderate-to-severity hot flashes and total hot flash severity score from baseline to 4 and 12 weeks of treatment, also documented by symptom diaries.

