- Additional secondary efficacy outcomes include changes in sleep quality, anxiety and depression symptoms, and menopause-related quality of life from baseline to 4 and 12 weeks of treatment, assessed using validated questionnaires.
- Additional safety outcomes include rates of severe headache, chest pain, and syncope, as well as all adverse events with a Common Terminology for Adverse Event Criteria severity grade of 3 or higher.

H. STUDY PROCEDURES

H.1 Screening and Baseline Evaluations

H.1.1 Schedule of screening and baseline evaluations

Screening evaluations will be conducted by study coordinators based at outpatient facilities on the Mt. Zion campus of UCSF or in rented facilities in surrounding counties, or through video-based assessments using UCSF's secure Zoom on-line video platform. Screening procedures will include a brief preliminary Screening Telephone Interview, followed by an in-person or video-based Screening Clinic Visit, completion of a 7-day hot flash diary at home, completion of a 3-day run-in period with 0.1 mg/hr NTG, and review of the diary and run-in medication tolerance at an in-person or video-based Baseline Clinic Visit.

All screening procedures must be completed within a 90-day period in order for participants to be eligible for randomization. If screening procedures cannot be completed within 90 days, initial screening procedures must be repeated to ensure that participant eligibility has not changed prior to randomization.

H.1.2 Consenting procedure

Prior to administration of any data collection instruments, signed consent will be obtained by a research coordinator at the beginning of the Screening Clinic Visit. A single informed consent process will be used that will cover both the screening and post-randomization procedures. All participants must be able to read and

understand the consent form in English and must provide written informed consent before enrolling in the study.

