Chest pain or tightness: Women reporting a history of coronary artery disease, diabetes, or two or more other major risk factors for coronary artery disease (smoking, hypertension, or hyperlipidemia with physician-recommended pharmacologic treatment) will be excluded from the study, to avoid the theoretical risk of increased chest pain or coronary events that could be associated with sustained transdermal nitrate therapy. Participants who have even one risk factor for coronary artery disease will undergo a screening ECG, and we will also exclude participants with evidence of myocardial infarction on screening ECG. Occurrence of chest pain severe enough to interfere with instrumental activities of daily living will be carefully monitored during the treatment period as part of the safety aim of the trial. Although the study team does not anticipate that many participants will develop severe chest pain interfering with daily activities, if any participant reports current or recent chest pain suggestive of ischemia at a study visit, she will be instructed to seek emergency medical attention. At the end of the treatment period, participants will be weaned off study medication rather than discontinuing medication abruptly, to minimize any risk of rebound chest pain.

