At each follow-up visit or phone call after initiation of NTG or placebo, blinded study coordinators will systematically assess for the following severe side effects that could be attributable to NTG therapy: 1) headache severe enough to interfere with instrumental activities of daily living; 2) chest tightness or pain interfering with instrumental activities of daily living, and 3) syncope (fainting or loss of consciousness). If reported, these symptoms will be recorded on standardized SAE or AE forms, depending on whether they meet the threshold for being an SAE or a non-serious AE. These standardized SAE and AE forms will indicate date of onset, date of resolution, likelihood of relationship to treatment, and actions taken in response to the event.

To collect information about other or unanticipated adverse events, participants will also be asked about any other negative changes in their health at each telephone and in-person follow-up contact after initiation of therapy, using the standardized question, "Have there been any changes in your health since your last visit or call?" Participants will also be given telephone numbers to call study staff in between scheduled study visits or calls if they wish to report any health changes in between scheduled study visits or calls. Any negative changes in health that are reported will again be recorded as AEs or SAEs using standardized forms, as appropriate.

Additionally, using the Common Terminology Criteria for Adverse Events (CTCAE) system, all adverse events will be graded in severity using the 5-point CTCAE scale. According to this scale, AEs are considered grade 1 if they represent only mild symptoms or asymptomatic laboratory findings; grade 2 if they cause moderate symptoms that limit instrumental activities of daily living (shopping, transportation, household tasks); grade 3 if they are serious or disabling events or result in hospitalization or prolongation of hospitalization without being directly life-threatening; grade 4 if they are life-threatening events in which the participant is at risk of death at the time of the event if immediate intervention is not undertaken; or grade 5 if they are fatal adverse events.

I.3.3 AE/SAE reporting procedures

A. SAE reporting

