headache during the first 24 hours of therapy, but no significant differences in rates of chest pain, syncope, or severe adverse events defined by CTCAE severity grade 3 or higher.

K.2 Data Analyses

K.2.1 Analyses for Objective 1

Analyses to address aim 1 will examine change in average daily hot flash frequency from baseline to 4 and 12 weeks of treatment, measured over 7 days by validated hot flash diaries (Sloan, Loprinzi et al. 2001, Food and Drug Administration 2003). The effect of NTG therapy will be estimated using linear mixed models (LMMs) for the repeated changes, adjusting for baseline values, under the assumption of an approximately constant treatment effects at 4 and 12 weeks; in supplementary analysis we will assess evidence for differences in the treatment effects at these two time points. The distribution of the LMM residuals will be assessed using Q-Q plots, and outcomes will be transformed if necessary to achieve approximate normality. Analyses will be by intention to treat, according to treatment assignment, and without regard to adherence.

K.2.2 Analyses for Objective 2

For additional confirmation of treatment effects on frequency of any hot flashes, we will also assess treatment effects on moderate-to-severe hot flashes and on total hot flash severity scores as secondary outcomes, also assessed by diary, using the same methods. The distribution of the LMM residuals will again be assessed using Q-Q plots, and outcomes will be transformed if necessary to achieve approximate normality. Analyses will again be by intention to treat, according to treatment assignment, and without regard to adherence.

K.2.3 Analyses for Objective 3

Analyses to address aim 2 will examine changes in sleep quality and duration, anxiety and depressive symptoms, and menopausal quality-of-life from baseline to 4 and 12 weeks. These outcomes will be captured by scores on validated self-administered questionnaires, with supplementation by sleep diary in the case of sleep duration. Intervention effects on these outcomes will be estimated using LMMs, adjusted for baseline scores. Approximate normality of the residuals will be checked using Q-Q plots, and outcomes will be transformed if necessary. Analyses will once again be by intention to treat and without regard to adherence.

K.2.4 Analyses for Objective 4

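### The prompted chest-pain question and the K.2.4 outcome cover only activity-limiting pain, while Hypothesis 4 carries no such limit, so milder chest pain may be under-recorded

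*Combined protocol and SAP*

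**What the plan says.** The plan describes chest pain in several places, and the terms differ.

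- **Prompted question (G.1.3 B and I.3.2).** At every visit or call after treatment starts, blinded coordinators ask about three symptoms. The second is "2) chest tightness or pain interfering with instrumental activities of daily living".
- **Monitoring statement (I.1.2, chest pain or tightness).** This uses the same threshold: "Occurrence of chest pain severe enough to interfere with instrumental activities of daily living will be carefully monitored".
- **Analysis (K.2.4).** The chest-pain outcome is pain or tightness that limits activities of daily living. K.2.4 also compares rates of all adverse events at any severity, and it uses Fisher's exact test for rare outcomes.
- **Hypothesis 4 (K.1, and in near-identical terms B.2 C).** It expects "no significant differences in rates of chest pain, syncope, or severe adverse events defined by CTCAE severity grade 3 or higher". Chest pain has no qualifier here.
- **Safety outcomes (G.2).** These include "rates of severe headache, chest pain, and syncope". The adjective may govern headache alone or all three symptoms.
- **Referral rule (I.1.2).** It applies "if any participant reports current or recent chest pain suggestive of ischemia at a study visit". Its qualifier is suspected ischemia, not activity limitation.

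Two other routes can bring in milder chest pain. Participants "will be instructed to contact study staff in between study visits to report any chest pain suggestive of cardiac ischemia" (G.1.3 B). Coordinators also put an open question about changes in health at each contact (G.1.3 C and I.3.2).

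**The concern.** Coronary risk under nitrate tolerance is the main theoretical harm in I.1.1, and it is the reason for the coronary exclusions. I.1.1 also says that no longitudinal human data exist on the cardiovascular consequences of chronic nitrate therapy. The ECG is done at screening only, and only in women with a cardiovascular risk factor (H.1.3 B, Appendix A). During treatment, symptom report is therefore the only scheduled signal of coronary ischemia.

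The direct question sets a functional threshold on that signal. Chest tightness can be brief and leave daily tasks unaffected, yet still belong to the outcome that Hypothesis 4 names, or be of the kind the referral rule is meant to catch. Hypothesis 4 predicts no significant difference, so any loss of events in the comparison it describes favors the predicted result.

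**Working it through.** The plan states no chest-pain rate, capture rate or power for a safety comparison, so there is no figure to reproduce. The check is first textual and then a hypothetical calculation.

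**Step 1: where the prompt starts on the plan's own severity scale.** I.3.2 describes grade 1 as mild symptoms and grade 2 as moderate symptoms that limit instrumental activities. The prompted question requires interference with instrumental activities. It therefore starts at about grade 2, and no question is directed at grade 1 chest pain.

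**Step 2: what each section counts.**

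- Prompted question, and monitoring statement in I.1.2: chest pain that interferes with instrumental activities.
- K.2.4: chest pain that limits activities of daily living (the word *instrumental* is absent).
- Hypothesis 4: chest pain. The same sentence does qualify headache (mild) and adverse events (grade 3 or higher).
- G.2: either severe chest pain or any chest pain.
- Referral rule and between-visit instruction: chest pain suggestive of ischemia.

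Question and analysis broadly agree with each other. Neither covers all of what Hypothesis 4 names.

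**Step 3: how a non-limiting episode reaches the database.** The open question is introduced this way: "blinded study coordinators will assess for other unanticipated adverse events at each follow-up contact using the standardized question". In I.3.2 participants are "asked about any other negative changes in their health at each telephone and in-person follow-up contact after initiation of therapy". Both are framed as being about events *other* than the three prompted symptoms, and the first is framed as being about unanticipated events, whereas chest pain is an anticipated one. The between-visit instruction names the symptom, but the participant must judge for herself that it may be cardiac. An episode reported by any of these routes is recorded, graded and counted in the all-adverse-event comparison. One that is not volunteered is not counted.

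**Step 4: hypothetical arithmetic.** Inputs: 70 per arm (K.3) and a two-sided Fisher test (K.2.4). The event counts are invented for illustration. With m events in total, the probability that k fall in one arm is C(70,k)·C(70,m−k)/C(140,m). The two-sided p sums the probabilities of all splits no more likely than the one observed.

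- 8 v 1 (m=9): 2 × (0.01509 + 0.00149) = 0.033.
- 4 v 1 (m=5): 2 × (0.15393 + 0.02903) = 0.37.
- 4 v 0 (m=4): p = 0.12.
- With no events on placebo, 6 on nitroglycerin are needed for p<0.05 (p=0.028).

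The 8 v 1 split lies close to the threshold: 7 v 1 gives p=0.06 and 8 v 2 gives p=0.10.

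**Step 5: the same point as power.** The rates and capture shares are again assumed, with the same share captured in both arms. Power is the sum, over all pairs of binomial counts, of their probability where Fisher p≤0.05.

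- True rates 15% v 2%: 74% with all events captured, 54% with 75% captured, 27% with 50% captured.
- True rates 10% v 2%: 36%, 21% and 8%.

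This shows that an any-chest-pain comparison would be sensitive to incomplete capture. It does not show how incomplete capture would be.

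**The case against.** The strongest reply is that the question fits the outcome that is analysed. K.2.4 prespecifies activity-limiting chest pain, I.1.2 monitors the same thing, the G.1.3 B list is headed as severe side effects, and headache is held to the same threshold. Non-limiting pain is then outside the definition by choice, and the unqualified term in Hypothesis 4 is shorthand. This largely stands. A reader might infer that the planned K.2.4 chest-pain result is itself under-counted and pushed toward no difference. The documents do not support that, because for activity-limiting pain the question asks what the analysis needs.

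A reader might also infer that coordinators ask about nothing else, and that milder chest pain is lost. The documents contradict this too. The open question is asked at every contact, participants are told specifically to report chest pain suggestive of ischemia, grade 1 events have a place on the scale, and all adverse events are compared by arm.

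Finally, the illustrative rates are high for this trial. Eight of 70 is 11%. I.1.1 reports no chest pain in the 19-woman pilot, and the plan intends to enroll women at very low cardiovascular risk. That objection stands against any claim about likely size.

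What survives is narrower. The other routes rely on the participant volunteering the symptom, the open question is worded for other events, and the all-adverse-event comparison does not commit to a chest-pain result at any grade. Hypothesis 4 as written therefore has no matching direct question and no matching analysis.

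**Conclusion.** The point holds as possible under-ascertainment of non-limiting chest pain, together with an inconsistent definition of chest pain across B.2, K.1, G.1.3 B, I.3.2, G.2, I.1.2 and K.2.4. It is a cheap improvement to safety ascertainment, not a flaw in the planned activity-limiting comparison.

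Its size is unknown. The documents give neither a chest-pain rate nor the share of episodes that limit activities or would be volunteered. The 8 v 1 and 4 v 1 splits and the power figures are hypothetical. They also treat every uncaptured event as lost, although the other routes would recover some.

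A reader might take the contrast with the referral rule to mean that all chest pain should trigger referral. The text does not say so. That rule has its own qualifier, suspected ischemia, which matches the between-visit reporting instruction. The only point here is that the prompted question uses a different criterion.

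**What to change.** 1. In G.1.3 B and I.3.2, change the second prompted item to ask about any chest pain or tightness since the last contact. For each episode, record the CTCAE grade (already planned for all adverse events) and whether it limited activities.
2. In K.2.4, report any chest pain by arm alongside the planned activity-limiting chest pain.
3. Reconcile the wording. State in B.2 C and K.1 which chest-pain outcome Hypothesis 4 concerns, remove the ambiguity in G.2, and use one description of activity limitation in G.1.3 B, I.1.2, I.3.2 and K.2.4.

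Leave the referral and stopping rules unchanged. The planned activity-limiting outcome remains available from the recorded limitation. The cost is one reworded question, one item on an existing form, one more line in the safety table and a few more minor events to record.

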Following run-in, eligible women will be randomized in equal ratios to the NTG or placebo interventions using a computer algorithm with randomly permuted blocks of size 2 and 4. To ensure similar distribution of women of different menopausal stages in each group, randomization will be stratified by menopausal stage (i.e., postmenopausal vs late menopausal transition), although there will be no pre-set sample size threshold for any specific stratum. Within each category, randomization numbers identifying the supply of medication for each participant will be generated and then assigned sequentially in the order participants are randomized.

To avoid manipulation of randomization, standard allocation concealment procedures will be followed (Schulz and Grimes 2002). Randomization numbers will be pre-printed on medication foil packets and master packs, prepared by Clinical Trials Services. At baseline, after screening data have been reviewed and the principal investigator has confirmed eligibility, a coordinator will enter the date and participant ID into the randomization log next to the number that has not yet been assigned, and dispense a supply of the drug identified by the randomization number. To provide a check on validity, an analyst will check that the randomization dates and times follow the order of the sequence numbers.

Based upon randomization, participants will be given a supply of either 0.2 mg/hr NTG or placebo patches and will be instructed to apply their first patch that night and change their patches on a nightly basis, without any patch-free periods, until the 1-week visit.

C. Blinding

Consistent with a double-blinded design, participants, investigators, and any study staff who have contact with participants or role in assessing outcomes will be blinded to treatment assignment. Only the statistician responsible for generating the randomization scheme and the staff of Clinical Trials Services contracted to package the active and placebo patches will have access to treatment assignment. Unless stipulated by the Data & Safety Monitoring Board or required for management of a participant with a serious adverse event, assignment codes will not be broken until all participants have completed the study, the trial data are cleaned, and the dataset is locked.

H.2.5 Follow-up visits

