Under these assumptions, a sample size of 140 (70 per group) should provide an estimated 87% power in 2-sided tests with type-I error of 5% to detect an 20% greater reduction in hot flash frequency (or 1.8 hot flashes per day) in the active treatment arm relative to the control arm. This will correspond to a 50-55% decrease in hot flash frequency from baseline in the active treatment group, which has previously been described as a clinically important effect in prior hot flash research (Butt, Deng et al. 2007). Estimates account for correlation of the repeated measures and loss to follow-up of up to 15%, and indicate that power will remain $\geq 80\%$ even if actual effect size or other parameters are less favorable than expected. This sample of 70 per group will also provide $>80\%$ power in 2-sided tests with type-I error of 5% to detect a between-group difference in mean frequency of moderate-to-severe hot flashes of ~ 1.5 hot flashes per day, as well as ~ 3.3 points in hot flash severity scores.

K.4 Additional Statistical Considerations

K.4.1 Drop-out rates

Based on past experience, participant dropout levels are expected to remain under 15% over 12 weeks. The assumption of non-informative dropout will be examined by comparing the baseline characteristics and early post-randomization outcomes of participants who are lost to follow-up versus retained in the study. If drop-out rates differ substantially between groups, analyses will be adjusted for baseline covariates associated with retention. In sensitivity analyses, we will also use multiple imputation of missing outcomes under plausible informative missingness assumptions, along with standard methods for calculating summary estimates and confidence intervals, to assess the potential impact of loss to follow-up on treatment effect estimates (Schafer 1999).

K.4.2 Dose effects

In the event that an overall treatment benefit is detected over 12 weeks, we will conduct exploratory analyses to probe for differences in the magnitude of treatment effects by highest-achieved NTG dose, by testing for interaction between treatment assignment and highest-achieved NTG dose in a linear mixed model for change in hot flash frequency. This analysis will control for the main effect of highest achieved dose to control the placebo effect of this self-selected variable, as well as baseline factors that may confound it, such as age, body mass index, and baseline hot flash frequency or severity.

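### G.1.4 lets significant baseline differences guide covariate adjustment, and no section says whether this reaches the efficacy models in K.2.1 to K.2.3

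*Combined protocol and SAP*

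**What the plan says.** - **G.1.4** lists sociodemographic, medical and reproductive variables. Among the reasons for collecting them is to "guide statistical adjustments in the event that significant differences between groups are detected at baseline". It does not name an analysis, a test or a significance level.
- **K.2.1** sets out the primary analysis: "The effect of NTG therapy will be estimated using linear mixed models (LMMs) for the repeated changes, adjusting for baseline values". The baseline value is the only covariate named. K.2.2 and K.2.3 follow the same pattern, and none of the three mentions G.1.4.
- **K.2.1** also leaves one choice to the data: "outcomes will be transformed if necessary to achieve approximate normality". **K.4.1** has an adjustment rule of its own: "If drop-out rates differ substantially between groups, analyses will be adjusted for baseline covariates associated with retention".
- **H.1.4** says that "eligible women will be randomized in equal ratios to the NTG or placebo interventions" and that "randomization will be stratified by menopausal stage". Stage does not appear as a covariate in K.2.1.
- **H.1.4**, on blinding, says that "assignment codes will not be broken until all participants have completed the study, the trial data are cleaned, and the dataset is locked".

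No section ranks G.1.4 against K.2.1 or confines it to sensitivity analysis.

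**The concern.** If allocation is sound, any baseline difference between the arms has arisen by chance. Testing it therefore tells us nothing about whether the variable should be in the model. What makes a covariate worth including is its relation to hot flash frequency, and a significance trigger does not look at that. Employment or parity could enter because of a chance imbalance, while a strongly prognostic variable with a slightly smaller imbalance stays out.

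The stratification factor shows the mismatch. Permuted blocks of 2 and 4 within stage keep the arms within two women of each other in each stratum, so a significance test would not select menopausal stage. Yet stage is the one variable the design itself singles out.

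Timing adds to the problem. For the blinded team, the arms can be compared at baseline only after lock, when outcomes are available too. Because the wording is loose, the covariate set for an efficacy estimate could then be argued either way.

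**Working it through.** **1. The plan's own power figure.** Inputs from K.3: 70 per group, difference 1.8 per day, SD of change 4.5, correlation 0.55, loss up to 15%, two-sided 5%, stated power 87%.
- Evaluable per arm: 70 × 0.85 = 59.5.
- SD of a single value: 4.5/√(2(1 − 0.55)) = 4.743.
- SD of the mean of two follow-ups, adjusted for baseline: 4.743 × √((1 + 0.55)/2 − 0.55²) = 3.261. This takes the correlation between the two follow-ups as 0.55 too, which K.3 does not state.
- Power: 85.3%, within 2 points of 87%. The standardised effect is 1.8/3.261 = 0.55.

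This calculation counts only the gain from adjusting for baseline, so changing the G.1.4 rule leaves it as it is.

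**2. How often the trigger would fire.** G.1.4 A to C names about 17 items (5 + 5 + 7). Coronary disease and diabetes are exclusions under E.3, which leaves 15. Current use of listed hot flash drugs is also excluded, and the menstrual items overlap with each other and with the stratum, so 12 is a reasonable lower count. With k independent tests at an assumed 0.05 cut, P(at least one significant) = 1 − 0.95^k:
- k = 12: 46%
- k = 15: 54%
- k = 17: 58%

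Correlation among the items lowers these figures.

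**3. Type I error.** Simulation with 60 per arm, 12 covariates and 20,000 runs per setting. Three covariates are prognostic, sharing an assumed R² of the residual variance (none are prognostic when R² is 0).

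| R² | K.2.1 covariates only | G.1.4 rule, mechanical | Better of the two |
|---|---|---|---|
| 0 | 5.0% | 4.9% | 5.5% |
| 0.2 | 4.9% | 4.7% | 5.7% |
| 0.4 | 5.1% | 4.1% | 5.7% |

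With 119 analysed (140 × 0.85) and 15 covariates, one of them prognostic, the better-of-two rate falls as low as 5.3%.

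**4. Power.** Simulation with 119 analysed, effect 0.55 SD, 15 covariates of which one is prognostic with assumed correlation r, 4,000 runs:

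| r | Never adjust | G.1.4 rule | Prognostic covariate named in advance |
|---|---|---|---|
| 0.3 | 84.9% | 83.9% | 87.5% |
| 0.5 | 83.4% | 83.4% | 92.1% |

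The rule costs 84.9 − 83.9 = 1.0 point and 83.4 − 83.4 = 0 points against no extra adjustment. Naming the covariate in advance gains 87.5 − 84.9 = 2.6 and 92.1 − 83.4 = 8.7 points.

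A normal approximation agrees. The non-centrality is 0.55 × √(59.5/2) = 3.00 without the covariate, 3.00/√(1 − 0.3²) = 3.145 at r = 0.3, and 3.00/√(1 − 0.5²) = 3.464 at r = 0.5. These give power of 85.1%, 88.2% and 93.4%, so gains of 3.1 and 8.3 points.

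**The case against.** The strongest reply is that G.1.4 belongs to a measurements section and only gives reasons for collecting questionnaires. Section K is the analysis plan, and K.2.1 does not invoke G.1.4. A secondary or sensitivity adjustment fits the words as well as a change to the primary model does. This stands in part: a reader might infer that G.1.4 definitely rewrites the primary analysis, but the text does not say so. What it leaves is an open scope that no section closes. Nor is K.2.1 wholly fixed without G.1.4, given the transformation clause and the retention adjustment in K.4.1.

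Three larger claims about harm are also tempting and are not supported.
- **Inflated false positives.** The mechanical rule stays at or slightly below 5%. Only choosing between models raises the rate, and not by much.
- **Conditional bias caused by the rule.** If a covariate is left out at an imbalance of z = 1.9, the conditional false-positive rate is 7.7% (r = 0.3) or 12.2% (r = 0.5), since the test statistic is then N(r·z, 1 − r²). K.2.1 without G.1.4 has exactly the same rates. At z = 2.5 they would be 10.5% and 20.6%, and those are cases that G.1.4 would correct.
- **Lost power.** The gap of 3 to 9 points is measured against a model the plan never proposed. It is a forgone gain and not a loss from the planned 87%.

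**Conclusion.** The point holds as a defect of specification. G.1.4 states an unsound trigger for covariate choice, with no scope or threshold, and K.2.1 to K.2.3 do not limit it. The trigger would fire in roughly half of soundly randomised trials (46% to 58%). The effect on error rates is small: none on overall type I error if applied mechanically, and about 5.3% to 5.7% if the better model is chosen. Power against K.2.1 alone changes by about 0 to 1 point. The more substantial cost is that covariates are not settled in advance, so about 3 to 9 points of available power may go unused.

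The documents do not give the number of variables tested, the 0.05 cut, the independence of the tests, the prognostic correlations or the correlation between follow-ups. All are assumptions here. The sample size of 140 is not in question. The change should be made, but the trial does not depend on it.

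**What to change.** - **G.1.4:** delete the clause that ties adjustment to significant baseline differences. Present the baseline table descriptively, without p-values.
- **K.2.1 to K.2.3:** state that covariates are fixed before unblinding and used whatever the observed balance. They should be the baseline value of the outcome, menopausal stage as the randomisation stratum, and any other variable chosen now because it is expected to predict the outcome. Age and body mass index appear in K.4.2 as possible confounders of self-selected dose, which is not in itself a reason to include them here. They need a prognostic justification of their own.
- **Any adjustment prompted by observed imbalance:** label it as a sensitivity analysis, reported beside the pre-specified estimate.

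The cost is protocol and analysis-plan wording only. Sample size, visits and data collection do not change.
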